Clinical data and digital MR scans from the Specific Aims of this study will be de-identified and obtained for analysis from the clinical database maintained by the Alzheimer's Disease Research Center (ADRC) at Washington University via an electronically secure file transfer protocol (ftp). At Northwestern University, the data will be downloaded to a Pentium D based PC managed by [name]. The data will be physically secure and will have continuous power via a UPS and connection to an emergency power supply. The NMFF's internet security system secures its network from the Internet via firewalls and a network intrusion detection system. Analysis of the data will be conducted by the Principle and Co-investigator. The confidentiality of the participants at Washington University will be protected as indicated in the "Code Access Agreement" signed by the PI and Washington University personnel such that Northwestern University personnel will not have access to subject identifiers or a master code list under any circumstances (see attached code access agreement).

Specific Aims 1& 2 - Monitoring Disease Progression During Treatment with Donepezil and Memantine in Subjects with Very Mild-to-Mild DAT

a. Overall Design and Source of Subjects.

Changes in specific neuroanatomical markers will be compared over a two year period in four groups of subjects – Group 1) subjects with very mild (CDR 0.5) to mild (CDR 1) DAT that are untreated with either cholinesterase inhibitors or memantine, Group 2) subjects with very mild (CDR 0.5) to mild (CDR 1) DAT that are treated with donepezil, Group 3) subjects with

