The hippocampus, parahippocampal gyrus and cingulate gyrus have been selected as the neuroanatomical variables to be assessed during the proposed funding period based on a review of the literature and our own prior results. Explicit neuroanatomical rules were used to define the boundaries of these brain structures. To generate templates, structural boundaries were outlined using semiautomated routines that combine autotracing and manual tracing techniques available in Analyze™. Analyze™ permits the simultaneous viewing of any point in the scan from three orthogonal planes. Autotracing functions encircle a selected region of uniform density by enclosing all contiguous pixels of similar density. The selection of tissue of a particular density is then achieved by setting thresholds that define the brightness of the pixels in the area of interest. Surrounding tissue of a different density (threshold) is deleted from the picture, leaving only the tissue of interest. When autotracing fails to segment tissues of similar density, the tissue is manually traced.

d. MR Scanning Protocols and Image Preprocessing

MR scans will be collected at the baseline assessment and after two years using a 1.5T VISION system (Siemens Medical Systems) with a UNIX based host computer (Sun Microsystems), actively shielded gradients, and echo-planar capability. Subjects will be positioned on the table with their canthomeatal line perpendicular to the table; head position stability is facilitated with adjustable cushioned head supports. A standardization object is placed in the field of view on the left side of the head for each MR scan. Prior to the scan, the

procedure is explained in detail to each subject, and techniques to tolerate small spaces and avoid claustrophobia are described. The MRI scans do not involve the administration of any contrast agent.

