Recently, we have adapted these methods to specifically assess the rate of change in hippocampal shape over time (Wang, et al, 2003). From the pairs of MR images collected at different time points, the assessment of a change in the shape of the hippocampus over time is accomplished by mapping the transformations from the first time point onto the second time point via rigid-motion registration (rotation and translation). If no change in the shape of the hippocampus has occurred, the result of this transformation is an identity map (modulo rotation and translation). Conversely, any shape change that has occurred is defined as the deviation of the result of the transformation away from this identity map. To compare shape change in different groups of subjects, the covariance of the resulting transformation vector fields across all subjects is used, and shape change is assessed in each group by 1) obtaining a set of eigenvectors via the singular value decomposition of the covariance matrix, 2) computing coefficients associated with these eigenvectors for each subject, and 3) performing a MANOVA using the eigenvectors across all subjects. A post-hoc logistic regression is used to determine which of the eigenvectors are most discriminating of the groups being compared. Since the covariance of the shape change vector fields is empirical, repeat neuroanatomical data from nondemented (CDR 0) subjects are required in order to account for “normal” shape change during the analysis of shape change associated with DAT and its treatment.

f. Methods for Labeled Cortical Depth Mapping (LCDM) of the Parahippocampal and Cingulate Gyri

When the brain structure of interest is a subregion of the cerebral cortex (e.g., cingulate or parahippocampal gyrus), it is first necessary to create a segmentation of the various tissues (i.e., gray matter, white matter, and CSF) within that portion of the MR dataset, and in relationship to the geometry of the neocortex. We have recently developed specific algorithms for this purpose (see Figure 5).

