Variables to assess changes in structural volume, thickness, and shape (for the hippocampus) will be generated as described above. Bivariate correlations between changes in clinical and neuroanatomical variables will be estimated using non-parametric statistics (Spearman's rho). To assess whether observed bivariate relationships are independent of each other, a stepwise multiple regression model will be developed including all independent neuroanatomical variables and slope values for the CDR sum-of-boxes scores as the dependent variable.

To test **hypothesis 2** (*The rate of decreasing hippocampal and cortical volumes, thinning of the cingulate and parahippocampal cortices, and changing hippocampal shape will be equal in DAT subjects that are untreated and in DAT subjects that are treated with donepezil alone, but greater than the rate of volume loss, thinning and hippocampal shape change in DAT subjects that are treated with the combination of donepezil and*

memantine.), rates of change for the various neuroanatomical variables will be compared in DAT subjects that are untreated, that are treated with donepezil alone, that are treated with the combination of donepezil and memantine, and in nondemented comparison subjects. These analyses will be performed using simple difference scores (follow-up minus baseline) for volume and thickness variables. To compare rates of change in hippocampal shape across groups, a MANOVA using eigenvectors derived from the time 1-to-time 2 transformation covariance will be performed (see above). The distributional characteristics of each of these variables will be examined prior to hypothesis testing. Finally, non-parametric (Wilcoxon rank sum tests) statistics will be used to compare the groups.

i. Sample Size and Power Considerations

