For the testing of **Hypothesis 2**, we will be measuring the rate of change of neuroanatomical variables over time; therefore, the test-retest reliability for these variables must be high. To estimate the normative test-retest reliability of the neuroanatomical measures proposed in this application, we scanned eight healthy control subjects on two separate occasions approximately one month apart, and then estimated differences between volumes and surface contours of the hippocampus. At the first time point, the mean left hippocampal volume was 2,233 mm³ and the mean right hippocampal volume was 2,699 mm³; at the second time point, these volumes were 2,209 and 2,686 mm³, respectively. Using repeated measures ANOVA, there were no significant test-retest differences in these volumes (on the left $F = .14$, $p = .72$; on the right $F = .07$, $p = .80$) and the intraclass correlation coefficient between these two datasets was very high (ICC = 0.93). To compare the similarity of surface contours at the two time points, we then registered all the scans with respect to the template and then calculated the percent overlap of voxels. The average percent overlap in the eight subjects was 87.4%, which is comparable to the overlap achieved by a single expert performing repeated manual segmentations of the hippocampus from the same MR scan (Haller, et al, 1997). To test the reliability of shape assessment for the hippocampus, we generated the eigenvectors associated with this brain structure based on the eight control subjects at time point 1. The coefficients associated with these eigenvectors were then computed for each subject at both time 1 and time 2. The mean ICC for all eigenvector coefficients was very high - 0.89 (range of 0.83 to 0.94), suggesting very high repeatability. Finally, the standard deviation for the estimation of hippocampal volumes on the two occasions was 225 mm³, and an annual rate of decrease in hippocampal volumes was 2 mm³.

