Assuming that the between-group effect size for comparisons of the rate of change of neuroanatomical variables is moderate (i.e., 0.5 or higher), and if the correlations in neuromorphometric measures within our proposed sample sizes at the different time points continue to be high (i.e., > .75), changes in brain structure shapes of the magnitude observed to date (see Progress Report and Wang, et al, 2003), and volume decreases of 50 mm³ or greater over two years, would be detectable with greater than 85% power (Borenstein and Cohen, 1988; Kraemer and Thiemann, 1987).

HUMAN SUBJECTS

50 new subjects who meet NINDS-ADRDA criteria for probable AD (i.e. DAT), and who have been registered with the MDC for treatment will be recruited for participation in the project during the proposed

funding period. The age range of the subjects will be 50 to 80 years. Any subjects will be excluded if they have medical problems that would contraindicate treatment with donepezil or memantine or make administration of a MR scan or any other aspect of the protocol hazardous.

With regard to the inclusion of both genders and various minorities, the samples will be equally balanced for gender and include approximately 15% African-American subjects. This percentage is similar to the distribution of African-Americans who present to the ADRC and MDC. This distribution of subjects should also allow inclusion of gender as a covariate in data analyses.

2. Collected clinical data will include information about demographics, dementia symptoms, other behavioral disturbances, and performance on tests of cognition (i.e., the ADAS-Cog). In all cases, verbal or written information obtained directly from the patients and involved caregivers will be used. These evaluations will take place in an ordinary office setting. MR scan data will be collected according to established protocols at the Mallinckrodt Institute of Radiology at Washington University.

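### Hypothesis 2 is about rates of change, but its volume, thickness and shape comparisons ignore the actual time between scans

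*Combined protocol and SAP*

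**What the plan says.** The target is a rate. Section i (Sample Size and Power Considerations) says of Hypothesis 2 that "we will be measuring the rate of change of neuroanatomical variables over time", and section h restates the hypothesis in terms of rates.

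The planned measure is not a rate. For volume and thickness, section h says: "These analyses will be performed using simple difference scores (follow-up minus baseline) for volume and thickness variables". The groups are then compared by Wilcoxon rank-sum tests, which carry no covariate. For shape, section e specifies that "any shape change that has occurred is defined as the deviation of the result of the transformation away from this identity map", and section h enters the resulting eigenvectors in a MANOVA without a time term.

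The nominal interval is two years. Section a says that changes "will be compared over a two year period in four groups of subjects", and section d that "MR scans will be collected at the baseline assessment and after two years". Section a also has the second scan of anyone who leaves early taken when they leave. It draws Groups 1 and 4 from an existing archive and Group 2 from the earlier funding period, giving neither their scan intervals nor an acceptable window.

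In the team's earlier longitudinal study (Assessment of Disease Progression Using Neuroanatomical Markers), intervals averaged 2.0 years (1.0-2.6) in CDR 0.5 subjects and 2.2 years (1.4-4.1) in CDR 0 subjects. There the volume comparison was repeated with scan interval as a covariate. The Hypothesis 2 plan has no such step.

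**The concern.** A subject rescanned before two years has had less time to lose tissue, so the raw difference looks like slower atrophy. If mean interval differs between two drug groups, the excess or shortfall goes straight into the treatment contrast. A shorter interval in Group 3 would imitate the hypothesised benefit of adding memantine; a shorter one in Group 2 would hide it.

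The groups are not randomised and were collected in different periods, so nothing in the design balances interval. Equality rests on the two-year schedule having been kept in all of them, and the plan neither checks this nor corrects for it.

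**Working it through.** **Inputs from the documents**
- Untreated CDR 0.5 loss: 164 mm³ left and 236 mm³ right over a mean of 2.0 years.
- CDR 0 loss: 82 and 142 mm³ over a mean of 2.2 years.
- Earlier group effect on volume loss: F = 7.81 on 1 and 42 df, with 18 and 26 subjects.
- Section i: "the standard deviation for the estimation of hippocampal volumes on the two occasions was 225 mm³", and a correlation between time points above .75.
- Sizes: Group 2, 38 to 47; Group 3, about 40.

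**The plan's own figures.** F = 7.81 on 1 and 42 df gives p = 0.0078, matching the stated 0.008. Section i also says that "volume decreases of 50 mm³ or greater over two years, would be detectable with greater than 85% power". That power follows if the effect size of 0.5 is in single-occasion SD units: 0.5/√(2 × 0.25) = 0.71, giving 87-91% for Group 2 v Group 3. It does not follow from 50 mm³ with SD 225 and r = .75 (28-31%). Here 50 mm³ serves only as a yardstick.

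**Annual loss.** CDR 0.5: 164/2.0 = 82 and 236/2.0 = 118 mm³. CDR 0: 82/2.2 = 37 and 142/2.2 = 65 mm³.

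**False difference per 0.1 year.** 0.1 × 82 = 8 mm³ and 0.1 × 118 = 12 mm³, or 16-24% of 50 mm³.

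**SD of two-year change, two estimates**
- 225 × √(2 × (1 − .75)) = 159 mm³. This is an upper limit, since the plan assumes r above .75.
- From the earlier study, assuming F refers to raw change averaged over sides: the difference is ((164 − 82) + (236 − 142))/2 = 88; 88/√7.81 = 31.5; 31.5/√(1/18 + 1/26) = 103 mm³.

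**False positives with no drug effect.** Simulated rank-sum test on raw differences, 47 v 40, two-sided 5%, normal errors, assumed within-group interval SD 0.3 years. Each range covers 82 to 118 mm³ per year.

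| Gap in mean interval | SD 159 | SD 103 |
|---|---|---|
| 0 | about 5% | about 5% |
| 0.1 year | 5-6% | about 7% |
| 0.2 year | 7-10% | 10-16% |

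Hand check, 0.2 years, SD 159, 82 mm³ per year: bias 16.4; spread √(159² + (0.3 × 82)²) = 161; standard error 161 × √(1/47 + 1/40) = 34.6; shift 0.47 standard errors; rejection about 7.6%.

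**Masking.** With a true sparing of 50 mm³ and Group 2 scanned 0.2 years earlier on average, the visible difference is 50 − 16 = 34 or 50 − 24 = 26 mm³. Rank-sum power falls from 27-29% to 11-16% (SD 159), or from 55-57% to 19-30% (SD 103).

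**If early-discontinuation scans enter.** Take 10 of 50 Group 3 subjects rescanned uniformly between 0.25 and 1.75 years, with all of Group 2 at two years. Group 3's mean interval is (40 × 2 + 10 × 1)/50 = 1.8 years, a bias of 16-24 mm³, with 7-10% (SD 159) or 10-14% (SD 103) false positives. If leavers decline 1.5 times faster, the bias is 8-12 mm³ and the rates are 5-6% or 6-8%. With similar early scans in Group 2 they are 3-5%; with completers only, about 5%.

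**Candidate remedies at a 0.2-year gap**
- Rank-sum on annualised change: 4-6% false positives, and in the masking case 24-27% (SD 159) or 52-54% (SD 103) power, whether the within-group interval SD is 0.3, 0.1 or 0.05 years.
- Regression of change on group and interval: false positives near 5%. The standard error rises up to about 6% at a within-group SD of 0.3 years, about 43% at 0.1, and more than doubles at 0.05, where power falls below that of the raw test. Interval is then nearly collinear with group.

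**The case against.** The strongest reply is that two years is the stated interval for all four groups, and at a common interval a difference is a rate times a constant. Section i supports this for Group 3: it describes the expected 40 as subjects with data for the full two years. Its one-year allowance concerns cognitive slopes, not scans. Completers-only is therefore the likelier reading for Group 3, and it gives no inflation from early leavers. This stands, although no section actually excludes the early scans, and it does not settle the archive and earlier-period groups.

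The one empirical check is also reassuring. Covarying interval in the earlier study moved p from 0.008 to 0.015 and left the conclusion unchanged. CDR 0 subjects had the longer mean interval, so a simple proportional-loss account would predict a larger adjusted contrast: annualised, 2 × (100 − 50.9) = 98 mm³ against 88 raw. The weaker p suggests either that interval and loss were only loosely related there, or that the F statistic was not on raw change. The second would undermine the SD of 103, and so the larger false-positive figures.

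Three stronger readings are tempting but unsupported:
- That the drug groups differ by 0.2 years. That gap is CDR 0.5 v CDR 0, and the overlap of those cohorts with Groups 1 and 4 is not stated.
- That Group 2 was rescanned at 48 weeks. That figure is the minimum availability of data for 38 subjects in an analysis of clinical slopes. Section a reports repeat scans for 38 Group 2 subjects but does not say that they are the same people or give a scan interval.
- That early scans will favour memantine. This needs them to enter the analysis, and to do so unequally.

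**Conclusion.** The omission is certain: a hypothesis about rates is tested on quantities that take no account of elapsed time, although the team adjusted for interval in its own earlier study. Its effect is conditional. It is zero at equal intervals and small at a 0.1-year gap. At an assumed 0.2-year gap, false positives are 7-10% (SD 159) or 10-16% (SD 103), or power for a 50 mm³ effect falls by roughly half.

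These figures assume loss proportional to time, normal errors and a within-group interval SD of 0.3 years. They concern hippocampal volume only; the same logic applies to shape and cortical thickness, but nothing is quantified for them. A reader should not infer that the Hypothesis 2 comparison is biased as it stands, because the intervals for Groups 1 to 3 are not given. The point is worth correcting because the correction is cheap and is best specified before the groups are compared.

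**What to change.** In section h:
1. Replace simple difference scores with annualised change (difference divided by actual years between scans) as the primary volume and thickness measure. Keep the planned rank-sum test.
2. As a sensitivity analysis, regress change on group with scan interval as a covariate. Give Group 4 its own interval slope, since nondemented subjects lose tissue more slowly (37-65 against 82-118 mm³ per year).
3. Add a sensitivity version of the shape MANOVA with scan interval as a covariate.
4. State one rule, the same for every group, on whether early-discontinuation scans enter, with a completers-only sensitivity analysis.
5. Report scan interval (mean, SD, range) by group.

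The cost is analysis wording plus one number per subject, from scans already held or planned; no identifiers need be transferred. Annualising has drawbacks: values from short intervals are noisier, and the test rejects 6-9% of the time if leavers who decline 1.5 times faster enter from one group only. The covariate model handles that case better (5-6%) but is unsuitable as primary while intervals are unknown, because its standard error rises about 40% or more when intervals are tight within groups (SD 0.1 year or less) but differ by 0.2 years between them.

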To determine whether cholinesterase inhibitors and memantine can slow the progression of disease in DAT subjects, we will use HDBM-LD and LCDM to compare the rate of change in the neuroanatomical measures listed above in three groups – 1) untreated DAT subjects, 2) DAT subjects treated with donepezil alone, and 3) DAT subjects treated with the combination of donepezil and memantine. Past, present and future subjects recruited from the ADRC as well as the Memory Diagnostic Center (MDC) at Washington University will be used for this study, and the period of treatment will be two years. Due to ethical considerations (see Research Design and Methods), drug treatment will be naturalistic and open label. **(Hypothesis 2: The rate of decreasing hippocampal and cortical volumes, thinning of the cingulate and parahippocampal cortices, and changing hippocampal shape will be equal in DAT subjects that are untreated and in DAT subjects that are treated with donepezil alone, but greater than the rate of volume loss, thinning and hippocampal shape change in DAT subjects that are treated with the combination of donepezil and memantine.)**

BACKGROUND

Cholinesterase Inhibitors as Treatments for DAT

Several cholinesterase inhibitors are now commercially available for the treatment of DAT, and have been shown to have at least ameliorative effects on the symptoms of DAT, including memory loss (Corey-Bloom, et al, 1998; Davis, et al. 1992; Farlow, et al, 1992; Knapp, et al, 1994; [name], et al, 1998; Rogers, et al., 1998; Rogers and Friedhoff, 1996; Thal, et al, 1996; Wilcock and Wilkinson, 1996). Cholinergic projections from the nucleus basalis are dispersed widely throughout the brain, and include the hippocampus, parahippocampal gyrus, cingulate gyrus and other neocortical areas. However, because of the central role played by the hippocampus and structures related to it in memory (Zola-Morgan and Squire, 1993), and the high frequency with which these structures are affected early in the course of Alzheimer's disease (Hyman, et al, 1984 and 1987; Arnold, et al, 1991; Gomez-Isla, et al, 1996; Berg, et al, 1998), these structures may be especially involved in symptom production and treatment response in subjects with DAT.

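### Hypothesis 2 predicts slower hippocampal shape change on the combination, but the planned shape test is an omnibus MANOVA that does not encode slower versus faster; a signed score and a named contrast should be prespecified

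*Combined protocol and SAP*

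**What the plan says.** Specific Aim 2 and section h of the combined protocol and SAP state the hypothesis with a direction. The rate of change in untreated and donepezil-alone subjects is to be equal, "but greater than the rate of volume loss, thinning and hippocampal shape change in DAT subjects that are treated with the combination" (that is, donepezil plus memantine).

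For volume and thickness, section h uses signed difference scores (follow-up minus baseline). For shape it says that "a MANOVA using eigenvectors derived from the time 1-to-time 2 transformation covariance will be performed". The groups listed are the three DAT groups "and in nondemented comparison subjects".

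Section e (HDBM-LD) describes the method as "performing a MANOVA using the eigenvectors across all subjects". It adds: "A post-hoc logistic regression is used to determine which of the eigenvectors are most discriminating of the groups being compared". It also says that repeat data from nondemented subjects "are required in order to account for “normal” shape change during the analysis of shape change".

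Section h closes with: "Finally, non-parametric (Wilcoxon rank sum tests) statistics will be used to compare the groups". It does not say which variables, which pairs of groups or which direction. Neither section defines a signed shape-change score, a contrast confined to the DAT groups, or a rule for deciding which group changed less.

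**The concern.** A MANOVA tests whether mean coefficient vectors are equal against any difference at all. Its power depends only on the squared distance between the means, so slowing, acceleration and a shift unrelated to disease count alike if they are the same size. The follow-up regression identifies which coefficients separate the groups, not which group progressed less.

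Two consequences follow. First, run on all four groups, the test can be significant purely because DAT differs from normal ageing, which says nothing about treatment. Second, a question about one direction is spread over about a dozen degrees of freedom, which costs power.

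Shape is a named component of Aim 2, and the treatment comparison is open-label and not randomised. A finding that the groups differ could be reported as slowing with no planned check on direction.

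**Working it through.** **Inputs.** Pilot longitudinal study (Preliminary Studies): 18 CDR 0.5 and 26 CDR 0 subjects, 12 eigenvectors, F = 2.66 on 12 and 31 df, effect size 2.0. Section a: Group 1 n = 21, Group 2 n = 38 to 47, Group 3 n about 40, Group 4 n = 44. Section e: enough eigenvectors for about 75% of variance, so the number is not fixed. Assumptions: two-sided alpha 0.05 (the plan states this for Hypothesis 1 only), normal data with equal covariances, and slowing expressed as a fraction of the DAT-minus-nondemented difference.

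**Step 1: reproduce the pilot effect.**
- T² = F·p·(N−2)/(N−p−1) = 2.66 × 12 × 42/31 = 43.25.
- D² = T²(1/18 + 1/26) = 43.25 × 0.0940 = 4.07, so D = 2.02, matching the stated 2.0.
- Bias-corrected: D² = (29/42) × 4.07 − 12 × 0.0940 = 1.68, so D = 1.30. The 95% interval for D is 0.36 to 2.21.

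**Step 2: reproduce the stated power.** Section i claims more than 85% for shape changes of the size seen so far. For two groups the noncentrality is D²·n₁n₂/(n₁+n₂), on p and N−p−1 df. For 38 v 40 with 12 eigenvectors, power is 1.00 at D = 2.02 and 0.97 at D = 1.30, so the claim reproduces for donepezil v combination. But that size is DAT versus nondemented. Between treatment arms it means that the drug abolishes the whole DAT excess.

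**Step 3: direction.**
- Three DAT groups, 12 eigenvectors, Group 3 differing by 0.5 SD: rejection 0.18 if slower, 0.19 if faster. At 0.707 SD: 0.39 and 0.38.
- Four groups with nondemented subjects included and no drug effect: rejection about 0.98 at D = 1.30 and 1.00 at D = 2.02.

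**Step 4: power for partial slowing.** Suppose that half of the disease-related change is removed, combination (40) v donepezil. At D = 1.30 the difference is 0.65, and the noncentrality with 38 donepezil subjects is (38 × 40/78) × 0.65² = 8.23 on 12 and 65 df.

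| Eigenvectors | D | Donepezil n = 38 | Donepezil n = 47 |
|---|---|---|---|
| 12 | 1.30 | 0.35 | 0.40 |
| 12 | 2.02 | 0.79 | 0.85 |
| 4 | 1.30 | 0.59 | 0.64 |
| 20 | 1.30 | 0.25 | 0.29 |

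**Step 5: a single score with an estimated direction.** The direction is trained on 21 v 44 archived subjects and tested on 40 v 38 at D = 1.30 with half slowing (simulation).
- Discriminant direction: about 0.56, whatever the coefficient variances.
- Raw mean-difference direction: about 0.64 if all coefficients have equal variance, falling to about 0.43 to 0.61 if variances decline, as they do for principal components. The result depends on which eigenvectors carry the signal.
- Rejection with no drug effect: about 5%.

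Every case exceeds the 0.35 of the 12-eigenvector MANOVA.

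**The case against.** A reader might infer that a significant shape result cannot support Hypothesis 2. That is true of the p-value alone. In the pilot the team read direction from displacement maps, which showed more widespread inward change in CDR 0.5 than in CDR 0 subjects. Group mean coefficients can also be set against the nondemented reference. The arbitrary sign of an eigenvector is no obstacle, since a flip reverses every group together, and eigenvector 1 correlated with volume change (r = −0.75). This stands, but the reading is descriptive: it has no planned contrast and no error control.

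A reader might also infer that real slowing will usually be missed. The documents do not establish that. Power for half slowing runs from 0.25 to 0.85 across the cases in the table, and the number of eigenvectors is not fixed.

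Nor is equal power for slowing and acceleration peculiar to MANOVA, since a two-sided test on a single score shares it. The score's advantage is a sign that can be read.

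Finally, volume and thickness already have signed scores, the CDR sum of boxes is the declared primary outcome, and the MANOVA is the team's established method. These points limit the severity. They do not supply the missing shape contrast.

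**Conclusion.** The point holds: followed as written, the plan does not answer the shape part of Hypothesis 2. The only test named for shape does not distinguish slower from faster change. With nondemented subjects in the model it is nearly always significant without any drug effect. This should be fixed, but it does not invalidate the study.

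The power cost is real but depends on the assumptions. For half slowing with 12 eigenvectors, a discriminant score raises power from 0.35 to about 0.56 at D = 1.30 (40 v 38). At D = 2.02 the MANOVA itself reaches 0.79 to 0.85. The calculation also assumes that the pilot distance, measured in CDR 0.5 subjects, carries over to groups that include CDR 1. The case for change rests mainly on direction and only secondarily on power.

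**What to change.** In section h, make the shape test for Hypothesis 2 a signed progression score:

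- Before any Group 3 follow-up scan is processed, fix the disease-change direction from the archived Group 1 and Group 4 change fields. This includes the eigenvector basis and the number retained. Use a discriminant or variance-standardised direction rather than the raw mean difference.
- Project each DAT subject's change onto that direction. Compare Group 3 with Group 2 on the score, with an estimate and confidence interval.
- For contrasts that involve Group 1, compute each Group 1 subject's score from a direction trained without that subject.
- Keep the MANOVA as a secondary test of any difference, restricted to the DAT groups when it is used to compare treatments.

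The cost is one paragraph and a few lines of code, with no new data. The downside is that the score is insensitive to drug effects outside the disease direction; the secondary MANOVA still covers these.
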